9. WHO Recommendations for the Prevention and Treatment of Postpartum Haemorrhage. Geneva: World Health Organization; 2012.
10. WOMAN Trial Collaborators. Effect of early tranexamic acid administration on mortality, hysterectomy, and other morbidities in women with post-partum haemorrhage (WOMAN): an international, randomised, double-blind, placebo-controlled trial. Lancet. 2017 Apr 26.

Research Design:

a. General Approach: Prospective Cohort study

b. Description: Phase 4

c. Methods: One Arm

d. Statistical Analysis:

- SPSS software will be used for our statistical analysis. Normal distribution will be assumed given the intended number of patients for analysis. Categorical variables will be analyzed using the Chi-square test. The t-test will be utilized for the comparison of continuous interval data.

-Using postpartum hemorrhage rate of 2.86% (institutional data), and a desired impact of reducing the hemorrhage rates by 50% after implementation of the new protocol, then 890 subjects would need to be recruited to answer the question.

e. Safety Analysis Plan:

- Data collection for each participant will occur in real time during pre and post delivery times, therefore safety monitoring of the patient and data will be simultaneous.
- A Research monitor has been appointed to oversee the safe and ethical conduct of the study. Additionally, the Research Monitor will provide review and comment on any adverse events. The Research Monitor is not a member of the investigative team. The role of the Research Monitor is as follows:
 1. monitor the consent process to ensure an absence of coercion
 2. monitor data collection/clinical outcome
 3. review all adverse event reports with comments from the PI and forward to the IRB with his/her own comments. Adverse events must be received by the IRB within 5 business days of occurrence or reporting (within 24 hours for serious adverse events)
 4. ensure the inclusion/exclusion criteria are followed
 5. review data security measures
- Any emerging safety concerns to include any adverse event rate higher than this institution's historical average will result in a halt to the study.

Subject Population:

Pregnant women presenting for delivery at NMCSO

a. Exclusion/Inclusion criteria:

Exclusion:

- a. Age less than 18 years
- b. Planned cesarean hysterectomy
- c. Current anticoagulant use
- d. Subarachnoid hemorrhage
- e. Any active/current intravascular clotting (i.e. venous thromboembolic events)

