 2. For patients that present for delivery at a gestational age less than 34 weeks, it will be recommended that they discard their breast milk until 24 hours after their last TXA administration.
 3. Order TXA for patient in ESSENTRIS
 4. RN to pull TXA from Pyxis and put in patient's room
 5. TXA per protocol (see supplement A)
 6. The use of additional uterotonics or single additional dose of TXA is at the discretion of the delivering provider
 7. For patient monitoring protocol please see Supplement B.
 8. All neonates are monitored for a minimum of 24 hours either by the NICU or the Newborn Nursery. Vitals are taken every four hours. Weights and bilirubin levels are obtained daily. Daily physical exams are performed.
3. Data collection
 1. Participants will be assigned an individualized subject number upon their enrollment to the study.
 2. Participants will be followed from their enrollment into the study until six weeks postpartum.
 3. An Excel spreadsheet will be used to collect the variables as listed above.
 4. Once the variable collection is complete, the information will become de-identified.

5. Chart review will be performed to estimate institutional rates of the secondary outcomes in the 12 months preceding the initiation of the protocol.
4. Data Analysis
 1. SPSS software will be used for our statistical analysis. Normal distribution will be assumed given the intended number of patients for analysis. Categorical variables will be analyzed using the Chi-square test. The t-test will be utilized for the comparison of continuous interval data.
 2. Using a postpartum hemorrhage rate of 2.86% (institutional data), and a desired impact of reducing the hemorrhage rates by 50% after implementation of the new protocol, then 890 subjects would need to be recruited to answer the question.
 3. The secondary outcomes will also be tested against institutional rates. Institutional rates will be estimated by record sampling done at the time of data collection.

Experimental Procedures:

See supplement A

Research materials collected:

Variables to be collected:

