To satisfy these two areas of responsibility, the research monitor may discuss the research protocol with the investigators, interview study subjects, and consult with others outside of the project about the research. In the event a problem is identified, they have authority to stop a research protocol in progress, remove individual subjects from a study, and take whatever steps are necessary to protect the safety and well-being of subjects until the IRB can assess the monitor's report.

Research monitors are required to promptly report their medical monitoring and oversight monitoring observations and findings to the IRB or other designated official.

Data Collection Sheets

See attached Excel spreadsheet.

Objectives:

The obstetrics literature to date focuses on TXA use prior to non-emergent cesarean delivery or in response to hemorrhage. Data is lacking in the area of prophylactic use prior to vaginal delivery. The aim of this study will be to assess the ability of TXA to prevent postpartum hemorrhage.

Primary Outcome:

To assess the efficacy of TXA in reducing the incidence of postpartum hemorrhage when given prophylactically prior to all deliveries.

The American Congress of Obstetricians and Gynecologists published 'ReVitalize' in 2014 that defined postpartum hemorrhage as blood loss of ≥ 1000 cc or blood loss accompanied by sign/symptoms of hypovolemia to include blood transfusion within 24 hours following the birth process (includes intrapartum loss).

[figure not shown]
For the purposes of this study, postpartum hemorrhage will be defined as a blood loss of ≥ 1000 cc in addition to all patients requiring blood transfusion (even if blood loss is less than 1000cc).

Secondary outcomes:

Estimated blood loss (EBL) – measured in cubic centimeters. EBL will be decided upon by the delivery provider. All delivering providers at this institution have received formal instruction on estimation of blood loss and a visual aid is available at every bedside and in the operating room (see below).

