Rates of hysterectomy – the number of patients requiring hysterectomy divided by the total number of deliveries

Admission to the Intensive Care Unit (ICU) - the number of patients requiring admission to the intensive care unit secondary to excessive blood loss divided by the total number of deliveries

Neonatal outcomes – incidence of fetal anemia, infection, hyperbilirubinemia, neurologic outcomes, and neonatal intensive unit admissions

Maternal mortality – incidence of mortality

Additionally, postpartum hemorrhage risk assessment will be utilized to stratify patients with regard to primary and secondary outcomes.

- Patients will be risk stratified to one of three risk categories depending on admission and intrapartum risk factors
 - High Risk Factors:
 - Placenta previa/ low lying placenta
 - Suspected accreta or percreta
 - Platelet count <70,000
 - Active bleeding
 - Known coagulopathy
 - Two or more medium risk factors
 - Medium Risk Factors:
 - Prior cesarean delivery, uterine surgery, or multiple laparotomies
 - Multiple gestation
 - > 4 prior births
 - Prior obstetric hemorrhage
 - Large myomas
 - EFW >4000
 - BMI > 40
 - Hct < 30%
 - Chorioamnionitis
 - >24 hours on Oxytocin
 - Magnesium sulfate
 - Low Risk: all patients not falling in the medium or high risk categories

Importance to Navy Medicine:

Beyond the potential impact that this study has in the reduction of maternal morbidity and mortality, it can also allow for perspective into resource management. Some of the Navy Military Treatment Facilities (MTFs) have limited blood bank stock, and massive hemorrhages requiring ongoing transfusion of products can quickly deplete the entirety of the supply. If we can find a solution that will reduce the number of instances where transfusion is necessary we can help to preserve limited resources. Likewise, this preventive measure will also have the potential to (cost) reduce the need for additional uterotonics, personnel, supplies and ICU beds.

There will be no collaboration with outside institutions.

Supplement A: TXA Protocol Administration (Modified from the NMCS Maternal Child Executive Committee's Policy)

1. TXA comes in a 1000 mg/10 mL vial. Nursing staff will pull this from the Pyxis at the same time they bring Oxytocin into the L&D room.
2. Add 1000 mg (or 1 vial) of 1000 mg/10 mL to 100 mL normal saline (100 mg/mL)
 - a. Bolus: 1 gram IV over 10 minutes
 - i. Set infusion pump rate to 600 mL/hr

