3. Begin the TXA infusion directly following umbilical cord clamping for the intent of preventing postpartum hemorrhage.
 - a. The TXA may be run as a secondary line (i.e. is compatible with pitocin) per [name], Chairman of the Pharmacy Department
4. TXA should be administered in a separate IV line from blood products.
5. Two-person verification is required (this can be a second nurse or can be the physician or certified nurse midwife that is attending the delivery)
6. A single additional dose of TXA (1 gram IV over 10 minutes) can be repeated after 30 minutes if bleeding continues or if bleeding stops and then re-starts within 24 hours of the first dose (for a maximum dose of 2g in 24 hours). This additional dose is considered a treatment dose. This additional dose is not required by the study design, which is to assess TXA in the *prevention* of hemorrhage.

Supplement B: Patient Monitoring following delivery

1. After delivery patients will be observed on the Labor and Delivery floor for a minimum of one hour. Thereafter they will be transferred to the postpartum ward where they will be observed for a minimum of 24 hours.
2. The following physical assessments will be completed every 15 minutes x 1 hour , then every 30 min x 2 hours, then every 4 hours until discharge.
 - A. Vital signs: BP and pulse as above. Temperature Q1 hour (after 2 normal values will space to Q4 hours).
 - B. Fundal assessment: Placement and tone
 - C. Lochia assessment: Color, with or without clots, amount
 - D. Perineum assessment: Intactness (approximation of tissues/wound/lacerations), hematomas, swelling
 - E. Bladder assessment: Distention, voiding (noting/documentation of most recent void/amount, spontaneous/catheterization).
 - F. Any symptoms that the patient reports.
3. The nursing staff will immediately report any findings that are not within normal limits to the delivering provider or on-call provider:
 - A. BP systolic > 160 or < 100
 - B. BP diastolic > 90 or <50
 - C. Pulse > 100
 - D. Nausea, dizziness or SOB
 - E. Moderate to copious lochia
 - F. Increased swelling or pain in vagina or perineal/rectal area
 - G. Distended bladder not relieved by catheterization or patient voiding
 - H. Fundus displaced or above umbilicus (if differs from initial normal placement of uterus), unrelieved with empty bladder.
4. Documentation
 - A. All assessments are documented in Essentris. See below for notes needed:
 - B. Complete intake and output flow sheet

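### Neonatal outcomes settled at birth precede TXA under Supplement A, yet are tested against historical rates with the other secondary outcomes; they should be separated as negative controls

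*Combined protocol and SAP*

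**What the plan says.** The Secondary outcomes section lists, without definitions or time windows, "incidence of fetal anemia, infection, hyperbilirubinemia, neurologic outcomes, and neonatal intensive unit admissions". Study Procedures, Data Analysis item 3, then states: "The secondary outcomes will also be tested against institutional rates". Neonatal outcomes are not exempted. The rates come from a chart review of the 12 months before the protocol starts, by record sampling of unstated size. Research Design describes one arm.

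On exposure, Supplement A item 3 reads: "Begin the TXA infusion directly following umbilical cord clamping for the intent of preventing postpartum hemorrhage". The Primary Outcome instead describes TXA "when given prophylactically prior to all deliveries". Implementation on L&D recognises breast milk as a route: for deliveries before 34 weeks, "it will be recommended that they discard their breast milk until 24 hours after their last TXA administration". It also provides that "All neonates are monitored for a minimum of 24 hours either by the NICU or the Newborn Nursery", with daily weights, bilirubin and examinations. Follow-up is longer: "Participants will be followed from their enrollment into the study until six weeks postpartum".

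The only stratification is by maternal hemorrhage risk category. Under the Safety Analysis Plan, any adverse event rate above the institution's "historical average will result in a halt to the study".

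**The concern.** An outcome can respond to a drug only if it is settled after exposure begins. If a singleton's cord is clamped before the infusion starts, the infant can be exposed only through milk. Fetal anemia is prenatal by name. An admission decided by the infant's condition at birth does not depend on a later maternal infusion. Testing these events against history examines whether the two sets of deliveries differ, not whether TXA does anything.

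The enrolled women may well differ from the preceding year's deliveries. Women with renal disease, autoimmune disease, heart failure, seizure disorder or thrombotic risk are excluded. Recruitment is in English and runs through prenatal registration, diabetes classes and unit tours. No passage says that the same eligibility rules apply to the sampled records. Neonatal rates could therefore move in either direction with no drug effect. What is at stake is the meaning of the neonatal comparison; the primary outcome is unaffected.

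**Working it through.** **Step 1. Place each listed outcome relative to exposure** (Supplement A timing, singleton).

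| Outcome | Can it follow TXA exposure? |
|---|---|
| Fetal anemia | No, if it means a prenatal condition |
| NICU admission decided by condition at birth | No; it is settled without any milk exposure |
| Later NICU admission | Yes, through milk |
| Infection, hyperbilirubinemia, neurologic outcomes | Yes if onset is later; no if present at birth |

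The list thus mixes events that cannot respond with events that might, and the plan gives no onset window to separate them.

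**Step 2. Look for an adjustment.** None is stated for neonatal risk. The hemorrhage risk categories include some relevant factors, such as multiple gestation and chorioamnionitis, but not gestational age, and they combine these factors with purely maternal ones. Gestational age, number of fetuses, birth weight and mode of delivery are on the list of variables to be collected.

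**Step 3. The plan's own figure.** The sample size of 890 concerns the primary outcome. A one-sample calculation with p0 = 0.0286 and p1 = 0.0143, assuming two-sided 0.05 and 80% power (neither is stated), gives

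n = [(1.960·√(0.0286·0.9714) + 0.842·√(0.0143·0.9857)) / 0.0143]² = 890.

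This fits a historical rate treated as fixed. It neither supports nor weakens the present point.

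**Step 4. How small a shift would be declared significant?** The documents give no neonatal rate, so NICU rates of 5%, 10% and 15% are assumed, with one infant per woman.

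- Against a fixed rate, 1.96·√(p(1−p)/890) gives 1.43, 1.97 and 2.35 percentage points.
- The secondary rates are sampled rather than fixed. With an assumed 890 records, multiply by √2: about 2.0, 2.8 and 3.3 points.

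**Step 5. How often would case mix alone produce a significant result?** Assume the enrolled infants' rate p1 is 0.8 times the historical rate p0, with no TXA effect. With 890 in each group and p̄ the mean of p0 and p1,

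probability = Φ{[(p0−p1)·√890 − 1.96·√(2p̄(1−p̄))] / √(p0(1−p0)+p1(1−p1))}.

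For p0 = 0.10 and p1 = 0.08 this is Φ{(0.597 − 0.793)/0.404} = 31%.

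| Assumed historical rate | 890 records | 3000 records |
|---|---|---|
| 5% | 17% | 22% |
| 10% | 31% | 43% |
| 15% | 46% | 62% |

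At 0.7 times the historical rate, the 5% to 15% range is 35% to 81% with 890 records and 46% to 94% with 3000.

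**Step 6. Chance.** Five neonatal outcomes each tested at 0.05, if independent, give 1 − 0.95⁵ = 22.6% probability of at least one false positive. No multiplicity rule is stated.

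**The case against.** The strongest reply is that collecting infant outcomes for safety is ordinary practice, and that most of this list can arise after birth. The protocol recognises breast-milk exposure and observes infants daily. That stands: a reader might infer that every neonatal difference from history is case mix, but the documents support this only for events settled at birth. Even there, case mix is one explanation beside secular change, chance, and prospective collection set against record sampling.

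Second, the timing is not settled within the documents. The Primary Outcome wording conflicts with Supplement A. Multiple gestation is not excluded, and Supplement A does not say which cord, so in-utero exposure of a later-born infant is not ruled out. This also stands and limits the point to singletons under Supplement A.

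Third, a reader might infer that a difference would be reported as TXA benefit or harm, or would trigger the halt rule. The plan states only that outcomes are tested. The Benefits section claims no reduction in any of these neonatal outcomes, and no passage classes them as adverse events. Both readings go beyond the text.

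Fourth, the thresholds in Step 4 are generic, and nothing shows that the exclusions shift rates that far. If excluded women's infants had a 30% NICU rate (an assumption), the share f of deliveries removed would have to satisfy f = d/(0.30 − p + d), where d is the fixed-rate threshold. This gives about 5%, 9% and 14%. The documents give no prevalence to compare with these, so the figures in Steps 4 and 5 are illustrations, not estimates.

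Finally, an unadjusted historical comparator affects every outcome. That is true, but only for the at-birth outcomes is a drug effect excluded in advance, which is what makes them useful as a check.

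**Conclusion.** The point holds in limited form. For singletons, under Supplement A, fetal anemia, conditions present at birth and NICU admission decided at birth cannot be TXA effects, yet the plan tests them with the rest against historical rates and without stated neonatal adjustment. The later-onset outcomes are not affected by this argument.

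The size cannot be fixed from the documents. On the assumed rates, a case-mix ratio of 0.8 with 890 sampled records gives a significant difference in 17% to 46% of studies with no drug effect. The logical part of the conclusion needs no rate; it rests only on the Supplement A timing. If reconciliation moved the infusion before delivery, the negative-control label would fail.

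**What to change.** 1. In Secondary outcomes, split the neonatal list into conditions present or decided at birth and conditions of later onset, with a definition and time window for each. State whether fetal anemia means a prenatal condition.
2. Treat the at-birth group as negative-control outcomes. A difference from history there indicates that the cohorts are not comparable and is not attributed to TXA. Absence of a difference is weak reassurance, given the thresholds in Step 4.
3. Report the later-onset group as safety outcomes in all infants, adjusted for gestational age, number of fetuses and mode of delivery, and abstract the same variables from the historical records. Feeding is not among the listed variables. Any analysis by milk feeding should be supplementary at most, because sick infants feed later and the restriction would select on health.
4. Reconcile the Primary Outcome wording with Supplement A, including which cord applies in multiple gestation.
5. Clarify whether neonatal events count as adverse events under the halt rule. No change to that rule is proposed here.

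The cost is protocol wording, classification by onset of records already being reviewed, and three case-mix variables from the historical charts. The drawback is that the negative-control label depends on the reconciled timing.

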Age, race/ethnicity, DoD status, BMI, gestational age, # of fetuses, gravidity, parity, admission diagnoses, admission estimated fetal weight, intrapartum diagnoses, postpartum diagnoses, misoprostol use, oxytocin use, mechanical dilation, duration of labor, magnesium sulfate use, planned mode of delivery, mode of delivery, birth weight, indication for operative delivery, neonatal outcomes, maternal outcomes, admission to the intensive care unit, uterotonic use, mechanical tamponade, blood product transfusion, estimated blood loss, qualitative blood loss, cumulative blood loss, laboratory results, post-delivery laboratory results

Confounding variables:

Management of the 3rd stage of labor

Source of the data:

Outpatient records (AHLTA), Inpatient records (Essentris). As providers, the investigators have access to these systems as a standard of care for patients receiving care from investigator-providers.

Paper records created in the Labor and Delivery department during the course of a delivery.

The data collected will be measured against the historic PPH rates of NMCSO over a period of time to be determined.

Protection of Privacy:

Each participant will be given a unique study number. A master list with only the minimal Personal Identifiable Information (PII) needed for follow up and their study number will be kept in the PI's office on a CAC PIN protected computer in the PI's locked office. The master list will be used to track the results of the study participant's data collection.

An Excel spread sheet will be used to collect this information using only the participants unique study number and stored electronically on a CAC PIN protected computer in the PI's locked office.

All data and PII will be destroyed (shred or deleted) at the conclusion of this project.

Risks:

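### Outcomes are to be stratified by hemorrhage risk, but the plan specifies no historic comparator by risk category, no historic PPH rate by delivery mode and no case-mix adjustment

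*Combined protocol and SAP*

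**What the plan says.** Research Design gives the design as "c. Methods: One Arm". The statistical paragraph there, repeated under Study Procedures (Data Analysis), takes a single institutional PPH rate of 2.86%, aims to halve it, and concludes "then 890 subjects would need to be recruited to answer the question". The only tests named are chi-square for categorical data and the t-test for continuous data.

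The historic comparator is described in two places:

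- **PPH** (Source of the data): "The data collected will be measured against the historic PPH rates of NMCSO over a period of time to be determined".
- **Secondary outcomes** (Study Procedures, Data collection, item 5): "Chart review will be performed to estimate institutional rates of the secondary outcomes in the 12 months preceding the initiation of the protocol". Data Analysis item 3 adds that these rates come from sampling records.

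The paragraph closing the Secondary outcomes section then says "Additionally, postpartum hemorrhage risk assessment will be utilized to stratify patients with regard to primary and secondary outcomes", and defines high, medium and low risk from admission and intrapartum factors. Two secondary outcomes have mode-specific denominators: surgical intervention per vaginal delivery and reoperation per cesarean delivery. The primary outcome pools all deliveries. The only confounder listed is management of the third stage of labor.

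**The concern.** With no concurrent control, a PPH rate in high-risk treated women says nothing about TXA unless there is a rate for comparable untreated women. The plan defines the risk categories for participants but does not say that past deliveries will be classified the same way.

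The same gap affects the overall comparison. Participants are women who consented and passed a long exclusion list, which is not stated to apply to the historic records. One of those exclusions, planned cesarean hysterectomy, bears directly on bleeding risk. If participants differ from past deliveries in delivery mode or risk, the crude PPH rate moves without any drug effect, and the planned tests cannot separate the two. Fixing the historic period, the eligibility rules and the PPH definition would not by itself equalise the mix.

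The Objectives also give as motivation that "Data is lacking in the area of prophylactic use prior to vaginal delivery", yet no comparison of PPH in vaginal deliveries is specified.

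**Working it through.** **1. The plan's own figure.** For one proportion against a fixed rate,

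n = [z_a·√(p0(1−p0)) + z_b·√(p1(1−p1))]² / (p0−p1)²

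with p0 = 0.0286 and p1 = 0.0143 (both from the plan). Alpha and power are not stated, so I assume two-sided 5% and 80%:

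n = (0.32669 + 0.09992)² / 0.0143² = 889.99, that is 890.

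This reproduces the stated figure. (One-sided 5% with 90% power gives 889.) Either way, the primary comparison was sized against one fixed, unstratified rate.

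**2. Rejection rule.** With n = 890, 15 events give z = (15/890 − 0.0286)/√(0.0286·0.9714/890) = −2.10, and 16 give −1.90. A significant reduction therefore needs 15 or fewer events. By the exact binomial, P(X ≤ 15) is 1.7% at 2.86%, and power at 1.43% is 79%. Expected events are 890 × 0.0286 = 25.5, or 12.7 if halved.

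**3. Delivery mode (assumed inputs).** The documents give no cesarean share and no mode-specific rates. Assume 25% historic cesareans, PPH 7% after cesarean and 1.48% after vaginal delivery: 0.25 × 7% + 0.75 × 1.48% = 2.86%. If participants have cesarean share s and TXA does nothing, their expected rate is 0.0148(1−s) + 0.07s.

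| Cesarean share of participants | Expected rate, no effect | Change from 2.86% | Chance of a significant reduction |
|---|---|---|---|
| 25% | 2.86% | 0 | 1.7% |
| 20% | 2.58% | −10% | 5.0% |
| 15% | 2.31% | −19% | 12.8% |
| 30% | 3.14% | +10% | 0.5% |

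At 30% cesareans, a true halving (3.14% to 1.57%) is detected with 67% power instead of 79%. If PPH after cesarean is instead 5% or 9%, with the overall rate held at 2.86%, the fall at a 15% cesarean share is 10% or 29%.

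**4. Risk category (assumed inputs).** Assume historic low/medium/high shares of 55/30/15%, PPH rate ratios of 1:2:5 scaled to 2.86%, and no effect. A cohort of 65/27/8% has an expected rate of 2.39% (−16%) and a 9.7% chance of a significant reduction. With ratios 1:1.5:3 and 1:3:8 that chance is 5.6% and 14.5%. A cohort of 50/30/20% has an expected rate 7% to 13% higher over the same ratios, which would hide an effect.

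**5. What strata could show.** With the historic shares and ratios of step 4, power to detect a halving within one risk category, even against a known stratum rate, is about 7% to 48% (exact, one-sided 2.5%).

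**6. Sampling error in the historic rate.** If the comparator is a sample of m records rather than a fixed 2.86%, the variance of the difference is p1(1−p1)/890 + p0(1−p0)/m. Normal-approximation power for a halving, 80% against a fixed rate, becomes 55%, 64%, 72% and 76% for m = 890, 1,780, 4,450 and 8,900.

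**The case against.** **Silence is not exclusion.** The plan does not forbid a stratified chart review, it speaks of historic rates in the plural, and the data-collection spreadsheet it mentions is not in the text available. This stands: the defensible statement is that these comparators are not specified. A reader might infer that no delivery mode will be taken from the historic records at all. The documents do not support that, because the two secondary outcomes with mode-specific denominators cannot be given historic rates without it. No such implication exists for PPH or for the risk categories.

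**Stratifying need not mean estimating an effect per stratum.** Also fair: descriptive reporting by risk category fits the sentence. It does not help the overall comparison, which stays crude.

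**Recruitment is broad.** A reader might picture a narrow set of volunteers from classes and tours. The plan also identifies women in antenatal clinics and on Labor and Delivery, and says everyone meeting the inclusion criteria will be offered the study. Selection by consent and exclusions remains possible, but its direction is not documented.

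**The sizes are assumed.** True. The 12.8% needs the cesarean share to fall from 25% to 15% at the same hospital, and nothing in the documents says it would.

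**The vaginal-delivery gap is background.** The stated aim covers all deliveries, so lacking a named vaginal comparison is a missed opportunity and not an internal contradiction.

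**Conclusion.** The point holds as a gap in specification. The plan stratifies outcomes by risk but specifies no historic risk classification, no historic PPH by delivery mode and no case-mix adjustment. Followed as written, it yields treated-only stratum results and a crude overall comparison open to bias in either direction.

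The size is unknown. Under the delivery-mode assumptions above, a 5- or 10-point lower cesarean share raises the chance of a spurious significant reduction from 1.7% to 5.0% or 12.8%. A 5-point higher share lowers it to 0.5% and cuts power from 79% to 67%. These figures show sensitivity to mix; they do not predict what will happen. A reader might infer that the study is biased toward finding a benefit, and the documents do not support that. The change is worth making because it is inexpensive relative to the ambiguity it removes.

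**What to change.** 1. Extend the chart review in Data collection item 5 so that each sampled historic delivery carries PPH by the study definition, delivery mode and the listed risk factors. Assign the same three categories and apply the study's exclusions.
2. Keep the crude comparison. As the main effect estimate, compare the participants' PPH rate with the historic rate standardised to their mix, Σ w_k·h_k, where w_k is the participants' share in mode-by-risk cell k and h_k the historic rate there. A regression on treatment period, delivery mode and risk category is an alternative if cells are sparse. Name the method in advance.
3. Give an interval that includes sampling error in the historic rate, state the number of historic records, and restate power on that basis.
4. Report comparisons by risk category and by mode, including vaginal delivery, with intervals and labelled descriptive, because 890 was sized only for the overall comparison with a fixed 2.86%.

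Supplement A starts the infusion after cord clamping. On that timing, delivery mode and the admission and intrapartum risk factors precede treatment and are legitimate adjustment variables.

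**Cost.** There is more abstraction per historic record (16 listed risk factors, plus delivery mode and PPH), a wider interval for the main estimate depending on the number of records, and wide intervals within strata. Participants' delivery mode and most of the risk information are already to be collected. Treatment, consent and enrolment do not change.
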